8.6. Treatment Compliance

Details of the date and time when the treatment is administered, along with any deviation from the procedure described in the Protocol, will be recorded in the subject's source documents and the eCRF. For the days subjects administer treatment at home, treatment compliance will be documented in a subject diary and will be assessed by the diary entries, including date, times, and whether the complete dose was administered, and returned treatment. Compliance for both clinic and home administration of treatment will be displayed in a data listing.

Treatment compliance will be summarized using the following parameter based on the data collected in the EDC:

- *Percent Compliance*, calculated as the total number of study drug administrations divided by total number of expected study drug administrations x 100. The total number of expected study drug administrations will be 20 for subjects who complete up to Day 10/Visit 3. For subjects who discontinued prior to Day 10/Visit 3, the total number of expected study drug administrations will be calculated as the last non-zero treatment administration study day during the treatment period x 2. For example, a subject who discontinued prior to Day 10/Visit 3 had his/her last non-zero study drug administration on study day 7, the total number of expected study drug administrations will be 14.

The above parameter will be summarized for each treatment group, for subjects in the Safety Population.

8.7. Protocol Deviations

In the event of a major protocol deviation, the Investigator and Sponsor's Medical Monitor and/or designee will determine whether the subject should continue to participate in the study. The Investigator should notify the IRB/IEC of deviations from the protocol or SAEs occurring at the site.

Protocol deviation management is detailed in the Protocol Deviation and Non-compliance Management Plan.

This document is confidential.

A data listing of all protocol deviations will also be provided.

This document is confidential.

9. Efficacy

All efficacy analyses will be performed using the Exploratory Efficacy Population unless specified otherwise. Subjects will be analyzed by cohort as members of the treatment group to which they were randomized.

9.1. Primary Efficacy Endpoint and Analysis

The primary efficacy endpoint is change from baseline in *P. aeruginosa* density (CFU/mL) as measured in induced sputum samples at 1 week after end of treatment (Visit 5/Day 17). The endpoint will be analyzed as logarithmic colony-forming units/mL sputum based on the Exploratory Efficacy Population (i.e., CFU counts will be transformed on a log10 scale prior to analysis and the calculation of change from baseline).

Cohort A and Cohort B will be analyzed independently. As there is no adjustment for multiple hypothesis testing only 95% confidence intervals comparing the two treatment groups will be calculated using a 2-sample t test with 0.05 significance level. No p-values will be calculated.

The following data will be excluded from the analysis:

- Data with missing *P. aeruginosa* density count.
- Data with qualitative results (i.e., not quantitative results) due to poor specimen quality.
- Data with specimen condition

A subject may have results from multiple isolates per timepoint. In such cases, *P. aeruginosa* density will be calculated as the sum of *P. aeruginosa* density from multiple isolates per subject per timepoint. Expectorated sputum sample data will not be used for analysis, but the data will be provided in a by-subject listing.

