4 SELECTION AND WITHDRAWAL OF SUBJECTS

4.1 Inclusion Criteria

Subjects who meet all of the following criteria will be considered eligible for enrollment in the study:

1. Are able and willing to comply with the Protocol and provide signed informed consent prior to any study-specific procedures;
2. Are male or female ≥ 18 years old;
3. Have a body mass index of $\geq 16.5 \text{ kg/m}^2$;
4. Have findings consistent with bronchiectasis per computerized tomography (CT) (or high-resolution CT [HRCT]);

Note: A CT or HRCT that demonstrates the above criterion is required during Screening or the Screening Period unless such an examination has been performed within the last 5 years and meets the above criterion.

5. Have microbiological evidence of pulmonary *P. aeruginosa* infection from a sputum sample within the last 24 months. Sputum cultures may be repeated on up to 3 occasions during the Screening Period to document *P. aeruginosa* presence if the initial sputum culture is negative;
6. Are willing and able to provide an induced sputum sample at Screening or during the Screening Period and at designated time points during the study and are willing and able to provide a spontaneously expectorated or induced sputum at all other time points;
7. Have $\geq 10^4$ colony-forming units of *P. aeruginosa* per gram of induced sputum obtained at Screening or during the Screening Period. Up to 3 specimens may be collected to meet this criterion;
8. Have forced expiratory volume (FEV₁) $\geq 35\%$ of predicted normal for age, gender, race, and height (using Global Lung Function Initiative standards) at Screening (regardless of the timing of the most recent prior administration of short-acting bronchodilator) or during the Screening Period;
9. Have, at the Baseline Visit, stable lung function, as determined by the Investigator, provided that the FEV₁ at the Baseline Visit has not decreased by more than 10% compared to the FEV₁ measured at Screening or during the Screening Period;
10. Have no acute infection or exacerbation of primary disease, as determined by the Investigator, prior to randomization and first dose of study drug;
11. Are able to reproducibly perform spirometry per American Thoracic Society/European Respiratory Society Standards;
12. Have past experience administering inhaled antibiotics and/or feel comfortable administering inhaled antibiotics and/or have a caregiver that is comfortable administering inhaled antibiotics to the subject;

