7 EFFICACY ASSESSMENTS

7.1 Efficacy Endpoints

The primary efficacy endpoint is sputum *P. aeruginosa* density as measured in sputum samples at 1 week after end of treatment for study drug (Visit 5/Day 17).

The phage recovery endpoint is based on AP-PA02 levels as measured in sputum and venous blood samples at time points specified in the Schedule of Assessments ([Appendix A](#)).

The exploratory endpoints include the following:

- Antipseudomonas antibiotic sensitivity of *P. aeruginosa* isolates at specified time points during the study;
- Change in *P. aeruginosa* density from Baseline;
- Change from Baseline of in vitro sensitivity of subject *P. aeruginosa* isolates to AP-PA02 and/or individual phage components;
- Change in spirometry from Baseline;
- Change from Baseline levels of sputum neutrophil elastase; and
- Change in quality of life as assessed by the following questionnaires:
 - Quality of Life-Bronchiectasis (QOL-B) Questionnaire;
 - Leicester Cough Questionnaire (LCQ); and
 - Saint George's Respiratory Questionnaire.

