9.2 Statistical Methods

9.2.1 Analysis of Efficacy

9.2.1.1 Efficacy Analyses

The primary efficacy endpoint is the sputum *P. aeruginosa* density as measured in sputum samples at 1 week after end of treatment for study drug (Visit 5/Day 17). The primary efficacy endpoint will be analyzed as logarithmic colony-forming units/g sputum based on the Exploratory Efficacy Population, and the treatment groups will be compared using a 2-sample t test with 0.05 significance level.

In addition, descriptive statistics will be calculated for the primary efficacy endpoint and all the other efficacy endpoints by treatment group based on the Exploratory Efficacy Population.

All statistical summaries will be descriptive in nature (eg, mean, standard deviation, median, minimum, and maximum for continuous variables and count and percentage for categorical variables). Further details, including the handling of missing data, will be specified in the Statistical Analysis Plan (SAP). The actual values and changes from Baseline will be summarized by visit using descriptive statistics, where appropriate, for all endpoints. Analysis details will be provided in the SAP.

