5.1. Primary Efficacy Endpoint

The primary efficacy endpoint is sputum *P. aeruginosa* density as measured in induced sputum samples at 1 week after end of treatment (Visit 5/Day 17).

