5.3. Exploratory Efficacy Endpoints

The exploratory endpoints include the following:

- Anti-Pseudomonas antibiotic sensitivity of *P. aeruginosa* isolates at specified time points during the study;
- Change in *P. aeruginosa* density from Baseline;
- Change from Baseline of in vitro sensitivity of subject *P. aeruginosa* isolates to AP-PA02 and/or individual phage components;
- Change in spirometry from Baseline;
- Change from Baseline levels of induced sputum neutrophil elastase; and
- Change in quality of life as assessed by the following questionnaires:
 - Quality of Life-Bronchiectasis Questionnaire;
 - Leicester Cough Questionnaire; and
 - Saint George's Respiratory Questionnaire.

This document is confidential.

6. Analysis Sets

Subjects who enrolled prior to the first DSMB meeting and received AP-PA02 were given a lower dose (3×10^{11} PFU/day) of AP-PA02. After the first DSMB meeting, a decision was made to increase the dosage of AP-PA02 to 6×10^{11} PFU/day (see [Section 8.5](#)). Unless noted otherwise, summary outputs by treatment groups will exclude subjects who were enrolled on the study prior to the first DSMB meeting that occurred on 01Nov2023 and received AP-PA02.

Subjects who were enrolled on the study prior to the first DSMB meeting but received placebo will be 'pooled' with the subjects who were enrolled after the first DSMB meeting as the 'pooled' placebo group within their respective cohorts.

All subjects will be included in the listings.

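### SAP 5.1 makes Day 17 density the primary endpoint and SAP 9.1 makes it change from baseline; adjusting for baseline gives one estimate under either definition, usually at little cost in precision

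*SAP*

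**What the plan says.** The places that define or analyse the primary endpoint are these.

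- **SAP 5.1** takes the level at the visit: *P. aeruginosa* "density as measured in induced sputum samples at 1 week after end of treatment (Visit 5/Day 17". It gives no unit.
- **SAP 5.3** puts the change in *P. aeruginosa* "density from Baseline" among the exploratory endpoints, and SAP 9.2.2 summarises it descriptively by visit.
- **SAP 9.1** states "The primary efficacy endpoint is change from baseline in" density at the same visit, in CFU/mL on the log10 scale. It analyses the cohorts separately, and "only 95% confidence intervals comparing the two treatment groups will be calculated using a 2-sample t test with 0.05 significance level". It plans no p-values and no baseline covariate.
- **Protocol 7.1**, in the version supplied, also takes the level: "density as measured in sputum samples at 1 week after end of treatment for study drug (Visit 5/Day 17".
- **Protocol 9.2.1.1** says the endpoint "will be analyzed as logarithmic colony-forming units/g sputum" and that the "treatment groups will be compared using a 2-sample t test with 0.05 significance level".

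SAP 6.2 already requires a non-zero baseline for every analysed subject. SAP 13 declares no change from the protocol's analysis. SAP 2 says that the SAP was written from protocol version 5.0.

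**The concern.** The same quantity, change in density to Day 17, is primary in one SAP section and exploratory in another, while a different quantity is primary in a third. The conflict lies inside the SAP, so it stands whichever protocol version applies.

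It matters because the interval is the main efficacy result: the trial has no power calculation and will report no p-value. With about 24 subjects per cohort randomised 2:1, chance differences in baseline density between arms will often be sizeable. An unadjusted level and an unadjusted change respond to such a difference in opposite directions. A report that moved from one definition to the other could show a visibly different result from the same data.

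**Working it through.** The documents give no SD, effect size or precision figure, so there is nothing of the plan's own to reproduce. Results are in units of the baseline SD.

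**Inputs.** About 24 per cohort at 2:1, so 16 vs 8 (SAP 4.3). SAP 6 drops AP-PA02 recipients enrolled before the first DSMB meeting and pools placebo, so 12 vs 8 and 8 vs 8 serve as illustrations of a smaller active arm. Two inputs are assumptions: ρ, the correlation between baseline and Day 17 log10 density (0.3 to 0.9), and k, Day 17 SD divided by baseline SD (0.8 to 1.5). The entry criterion of at least 10^4 CFU "per gram of induced sputum obtained at Screening or during the Screening Period" may narrow the baseline spread, so k above 1 is possible.

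**1. Gap between the two estimates.** Let d be the baseline mean difference between arms and f = 1/n1 + 1/n2. The Day 17 estimate minus the change estimate is exactly d, with SD √f.
- 16 vs 8: √(1/16 + 1/8) = 0.433; P(|d| > 0.5) = 2[1 − Φ(0.5/0.433)] = 0.248.
- 12 vs 8: √(1/12 + 1/8) = 0.456; the probability is 0.273.

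**2. How much imbalance each estimate carries.** Given d, the expected error of the Day 17 estimate is kρ·d and that of the change estimate is −(1 − kρ)·d. Over the assumed grid, 1 − kρ runs from 0.76 (k = 0.8, ρ = 0.3) through 0 (k = 1.25, ρ = 0.8) to −0.35 (k = 1.5, ρ = 0.9).

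Take k = 1 at 16 vs 8 and the roughly 12% of trials with d above 0.5, where d averages about 0.71. The mean error of the change estimate is −0.7 × 0.71 = −0.50 at ρ = 0.3 and −0.3 × 0.71 = −0.21 at ρ = 0.7. In simulation with no treatment effect, the change interval covers 88% and 92% of the time in those trials, and ANCOVA about 95%. Over all trials both cover about 95%.

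**3. ANCOVA gives one answer.** If Y = a + τT + βB + e, then Y − B = a + τT + (β − 1)B + e. The estimate of τ, the residuals and the interval are identical. Simulation agreed to about 1e-15.

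**4. Half-widths, with N = n1 + n2.**
- Change: t(N−2)·√[(1 + k² − 2ρk)f]
- ANCOVA: t(N−3)·√[k²(1 − ρ²)f]·√[1 + 1/(N−4)]

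Example at 16 vs 8, k = 1, ρ = 0.5: change 2.074 × 1 × 0.433 = 0.898; ANCOVA 2.080 × 0.866 × 0.433 × 1.025 = 0.799; ratio 1.12.

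Ratio of change to ANCOVA at 16 vs 8 (above 1 means that ANCOVA is narrower):

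| k | ρ=0.3 | 0.5 | 0.7 | 0.8 | 0.9 |
|---|---|---|---|---|---|
| 0.8 | 1.37 | 1.29 | 1.23 | 1.22 | 1.25 |
| 1 | 1.21 | 1.12 | 1.06 | 1.03 | 1.00 |
| 1.25 | 1.10 | 1.03 | 0.98 | 0.97 | 1.00 |
| 1.5 | 1.04 | 0.99 | 0.97 | 1.00 | 1.10 |

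The largest reductions in width are 1 − 1/1.37 = 27% (k = 0.8), 1 − 1/1.21 = 17% (k = 1) and 1 − 1/1.10 = about 9% (k = 1.25 or 1.5).

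**5. Least favourable slope.** Since 1 + k² − 2ρk = k²(1 − ρ²) + (1 − kρ)², ANCOVA compares worst at kρ = 1. Its width relative to the change interval is then [t(N−3)/t(N−2)]·√[1 + 1/(N−4)]:
- 16 vs 8: 1.0028 × √1.05 = 1.028
- 12 vs 8: 1.0042 × √(1 + 1/16) = 1.035
- 8 vs 8: 1.0073 × √(1 + 1/12) = 1.048

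These are averages over chance imbalance. At 16 vs 8 the factor from lost degrees of freedom and imbalance exceeds 1.03 in 28% of simulated trials, and its 95th percentile is 1.096.

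**6. Zero counts.** For one subject with a Day 17 zero, two substitution values 1 log10 apart (assumed) move the arm mean by 1/16 = 0.06 log10 in an arm of 16, or 1/8 = 0.125 in an arm of 8.

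**The case against.** The strongest reply is that SAP 9.1 is the operative section. It gives one computable analysis with a valid interval, so correcting 5.1 would remove the contradiction and leave ANCOVA as an efficiency preference in a Phase 2 trial without p-values. Much of this stands. A reader might infer that the change-score interval is wrong, or that the SAP gives no usable primary analysis; neither is so. What does not follow is that a wording edit settles everything, because the change estimate keeps (1 − kρ) times any baseline imbalance.

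A reader might also go too far the other way on four points.

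- *The change estimate carries the whole imbalance.* It would do so only if kρ = 0, which occurs nowhere on the grid. The full imbalance is the gap between the two estimates.
- *About 3% is the most that ANCOVA can cost.* It is an average at the least favourable slope for 16 vs 8. A single trial can lose more, and so can a smaller cohort.
- *Savings of 20% or more are typical.* They occur in 2 of the 20 cells, both at k = 0.8. ANCOVA is the wider interval in 7 cells, one of them (k = 1, ρ = 0.9) by only 0.2%.
- *The SAP departs from its protocol without saying so.* The unit and the SAP 13 entries depend on protocol version 5.0, and the supplied protocol is not confirmed to be that version.

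The coverage figures assume equal variances in the two arms. With residual SDs of 1.5 vs 0.75 (16 vs 8), both pooled intervals cover about 98%, so unequal variance does not favour either. Analysis as randomised is already in SAP 9. The list of excluded data in SAP 9.1 breaks off in the supplied text, so the lack of a zero-count rule can be stated only for that text.

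**Conclusion.** The inconsistency is certain: SAP 5.1 and 9.1 name different primary endpoints, and the one in 9.1 is exploratory in 5.3. It should be fixed before unblinding. The two estimates differ by the chance baseline difference (SD 0.43 baseline SDs, 25% chance of exceeding 0.5, at 16 vs 8 under normality).

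The case for baseline adjustment is good but conditional. It removes the part of the imbalance that the change estimate retains and gives one result under either definition. Its average price at the least favourable slope is 2.8% in width at 16 vs 8, 3.5% at 12 vs 8 and 4.8% at 8 vs 8, with a 95th percentile of about 10% for a single trial at 16 vs 8. The gain may be large, small or absent: in some cells with k above 1 the change interval is up to about 3% narrower. All precision figures rest on assumed ρ and k.

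**What to change.** 1. In SAP 9.1, within each cohort, estimate the treatment difference and its 95% CI by ANCOVA of log10 Day 17 density on treatment and log10 baseline density.
2. State one endpoint definition in SAP 5.1 and 9.1, and remove the overlap with 5.3.

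Secondary items:

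- State in advance how a zero or below-detection Day 17 count enters the log10 scale, and repeat the analysis with one other value. SAP 6.2 deals only with a zero baseline.
- Add a sensitivity analysis that keeps the major protocol violators whom SAP 6.2 excludes. Blinded review limits selection, but no planned analysis would show the effect of the exclusion.
- Check protocol version 5.0, reconcile the unit (CFU/mL in SAP 9.1, CFU/g in the supplied protocol) and list in SAP 13 any departures that apply.

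The cost is SAP wording, one model per cohort with one degree of freedom lost, and two short sensitivity runs. No new data or visits are needed, and the covariate loses no subject, because a baseline value is already required.

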7.2 Sputum Culture

Sputum for microbiology will be processed at a central laboratory for all visits. Quantitative cultures and sensitivity will be performed. *P. aeruginosa* isolates obtained from sputum samples at all visits will be frozen for possible future genotyping analysis. No subject (human) samples will be retained for any genetic analysis.

Collection of sputum via spontaneous expectoration or induction will be performed per standardized methodology at the time points specified in the Schedule of Assessments and Timing of Sample Collection and Procedures for the Treatment Period ([Appendix A](#)). Induced sputum samples for culture will be required at Screening, Baseline, Visit 2/Day 5, Visit 3/Day 10, Visit 4/Day 11, Visit 5/Day 17, Visit 6/Day 24, and Visit 7/EOS/Day 38. Standardized sputum induction methodology will be detailed in the Study Manual.

For expectorated sputum collection, subjects may be asked to provide first morning samples expectorated before a given clinic visit or the subjects may provide the expectorated sputum sample during the clinic visit. Samples collected at home by the subject should ideally be collected prior to administration of any inhaled antipseudomonal antibiotic. Subjects will be provided sputum collection containers and insulated transport containers in which to carry their specimens to the clinic.

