6.2. Exploratory Efficacy Population

The population for efficacy (clinical activity) analysis will consist of all subjects who receive any AP-PA02 or placebo with at least 1 non-zero Baseline measurement and 1 post-Baseline assessment for the primary efficacy endpoint. In addition, subjects with any major protocol violations that could influence the validity of the data for the primary efficacy evaluation will be excluded. All criteria to exclude subjects from the Exploratory Efficacy Population will be made based on a blinded review of the data prior to the unblinding of the study.

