7.1. General Methods

All analyses and summaries will be produced using Statistical Analysis System (SAS®) version 9.4 or higher. All SAS programs used to generate analytical results will be developed and validated according to [REDACTED] and SAS validation procedures. Summaries will be presented by treatment group unless otherwise specified.

Unless otherwise noted, continuous variables will be summarized using the number of non-missing observations (n), arithmetic mean (Mean), standard deviation (SD), median, minimum, and maximum values as summary statistics. The minimum and maximum will be displayed to the precision with which the data were collected. The mean, median, and quartiles will be displayed to one additional decimal place and the SD will be displayed to two additional decimal places, where applicable.

Descriptive statistics for categorical/qualitative data will include frequency counts and percentages. The total number of subjects with a non-missing value for the given variable will be used as the denominator for percent calculations, unless stated otherwise. All percentages will be presented with one decimal, unless otherwise specified. Percentages equal to 100 will be presented as 100, and percentages will not be presented for zero frequencies.

All relevant subject data will be included in listings. All subjects entered into the database will be included in subject data listings. Prior to database lock, the study statistician, data management lead, and medical monitor will review the data entered in the EDC to ensure that the database value falls within reasonable human measurements.

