7.3. Missing Data

In general, missing endpoint data will not be imputed. All analyses will be based on observed endpoints and related data. Sections 7.3.1 and 7.3.2 note the situations where missing data will be imputed.

This document is confidential.

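### The SAP log-transforms sputum counts but assigns no value to an adequate post-baseline culture with no growth, so culture-negative subjects can fall out of the primary interval

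*SAP*

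**What the plan says.** SAP 9.1 makes change from baseline in induced-sputum *P. aeruginosa* density (CFU/mL) at Visit 5/Day 17 the primary endpoint and specifies that "CFU counts will be transformed on a log10 scale prior to analysis and the calculation of change from baseline". Each cohort gets a 95% t interval for the treatment difference, with no p-value. SAP 9.2.2 uses the same transformation for the by-visit summaries and adds percent change.

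The other text that bears on a zero or no-growth count is:

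- Protocol 7.2, on the central laboratory: "Quantitative cultures and sensitivity will be performed". Neither document states a limit of detection or quantification for culture.
- SAP 6.2: the efficacy population is treated subjects "with at least 1 non-zero Baseline measurement and 1 post-Baseline assessment for the primary efficacy endpoint".
- SAP 9.1, exclusions: missing counts; "Data with qualitative results (i.e., not quantitative results) due to poor specimen quality"; and a third bullet on specimen condition, which is incomplete in the text available.
- SAP 9.1: "A subject may have results from multiple isolates per timepoint", in which case the densities are added.
- SAP 7.3: "In general, missing endpoint data will not be imputed". The exceptions it points to concern medication and adverse-event dates.
- SAP 7.1: "All analyses and summaries will be produced using Statistical Analysis System".

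SAP 6.2 also says that "subjects with any major protocol violations that could influence the validity of the data for the primary efficacy evaluation will be excluded". Protocol 9.1 contains neither this condition nor the non-zero Baseline condition, yet SAP section 13 records no change from the protocol.

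**The concern.** An adequate culture with no growth is the best microbiological result a subject can have, and it is the one result the stated derivation cannot process. The non-zero Baseline condition shows that zeros were foreseen, but no rule covers the visits at which treatment would produce them.

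Each cohort has about 16 active and 8 placebo subjects. There will be fewer on active, because SAP section 6 takes AP-PA02 subjects enrolled before the first DSMB meeting out of the summary outputs. A handful of records therefore matters. The 95% interval is the only planned between-group comparison of the primary endpoint. No power is claimed and no p-value is planned, so what is at stake is bias in the estimate and its interval.

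**Working it through.** **1. Follow one subject through the SAP.** Take a subject with growth at Baseline and an adequate Day 17 specimen with no growth.

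- SAP 6.2: the Baseline value is non-zero and a post-Baseline assessment exists, so the subject is in the population.
- SAP 9.1 exclusions: a zero is not plainly a missing count, and the result is not qualitative because of a poor specimen. The incomplete third bullet could bear on which records are removed, but an exclusion cannot supply a value.
- Summing rule: it covers several isolates, not none.
- Transformation: log10(0) is undefined, and SAS returns missing.
- SAP 7.3: missing endpoint data stay missing.

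The subject is in the population without a primary endpoint value. Any other result needs a choice that is not written down.

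**2. Inputs for the size.** From the documents: about 24 per cohort at 2:1, so 16 and 8. There is no stated effect, SD or limit to reproduce. Everything else below is assumed. Differences are active minus placebo in log10; *kept* means set to the limit, *dropped* means treated as missing.

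**3. All-or-none clearance.** Assume baseline 10^7 and limit 10^2, so a cleared subject kept at the limit changes by -5. Among subjects with growth, the mean change is -1 on active and 0 on placebo, with SD 1.

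*Four active and no placebo clearances:*

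- Kept: (12 × -1 + 4 × -5)/16 - 0 = -2.00. Pooled variance = (11 + 12 × 1² + 4 × 3² + 7)/22 = 66/22 = 3. Half-width = 0.898 × √3 = 1.56, where 0.898 = t(22) × √(1/16 + 1/8). Interval (-3.56, -0.44).
- Dropped: 12 vs 8, -1.00, interval (-1.96, -0.04).

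*Two active and one placebo clearances (12.5% each):*

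- Kept: (14 × -1 + 2 × -5)/16 - (1 × -5)/8 = -1.50 + 0.625 = -0.88, interval (-2.46, 0.71).
- Dropped: 14 vs 7, -1.00, interval (-1.97, -0.03).

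Dropping understates the effect in the first case and overstates it in the second. In general, let c be the baseline-to-limit gap, d the change in uncleared active subjects, and pa and pp the clearance rates. Then kept = -c·pa + d(1 - pa) + c·pp, and dropped = d. They agree when pp = pa(c + d)/c, which is 0.80 × pa for c = 5 and d = -1 (0.67 to 0.83 for c from 3 to 6).

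**4. Gradual shift.** Day 17 value e = baseline b + N(μ, SD), with no growth if e is below the log10 limit L. Kept = mean of max(e, L) - b; dropped = mean of e - b over e ≥ L; placebo shift 0. The simulations used 1,000,000 subjects per arm. Baseline mean was 6 to 8 log10, with SD 1 (with or without a 10^4 floor) or SD 1.5. The limit was 10^1 to 10^3 and the SD of change 1 to 2.

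| True shift | Dropped minus kept | Active subjects dropped |
|---|---|---|
| -1 | 0.00 to +0.14 | 0% to 20% |
| -2 | -0.04 to +0.28 | 0% to 33% |
| -4 | -0.63 to +0.45 | 2% to 76% |

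A positive gap means that dropping understates the reduction. For scale, the interval half-width at 16 vs 8 is about 0.90 × SD. A gap near zero does not show that little was lost: with baseline N(7,1), limit 10^3, SD 1 and true shift -4, both rules give -3.44 with 50% of active subjects dropped. Keeping results at the limit also attenuates large effects. With baseline N(7,1), limit 10^2, SD 2 and true shift -4, kept is -3.53 and dropped -3.10.

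**5. Dependence on the substituted value.** In the four-and-none example:

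- at the limit (100 CFU/mL): -2.00;
- at half the limit: (12 × -1 + 4 × -5.301)/16 = -2.08;
- at 1 CFU/mL: (12 × -1 + 4 × -7)/16 = -2.50.

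**6. Percent change of log10 values (SAP 9.2.2).** The same 99% kill (-2 log10) gives 100 × (-2)/8 = -25% from 10^8, 100 × (-2)/6 = -33% from 10^6 and 100 × (-2)/4 = -50% from 10^4. The figure depends on baseline and, through the log of the baseline value, on the units.

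**The case against.** A reader might infer that the SAP excludes culture-negative subjects. It does not: no passage says that zeros are dropped, and SAP 6.2 keeps these subjects in the population. What is missing is their value; dropping is what a literal run would do. A reader might also infer that the gap must work against AP-PA02. Step 3 shows that the direction depends on the clearance rates in both arms.

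Materiality is assumed, not shown. The large figures need all-or-none clearance or a shift near -4 log10. For shifts of -1 to -2 the gap is small beside the interval width. The two-and-one example builds in a difference of -1 among subjects with growth. It shows how an interval can move and is not a significance claim, since no p-values are planned. All of this stands and limits the weight of the point.

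The primary interval is not the whole reporting of density. Descriptive summaries, by-subject plots on the original scale and full listings are planned, so recorded clearances need not be hidden. That stands too, but those outputs do not change which subjects enter the interval.

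The central laboratory may report a numeric value at its limit, or a laboratory manual or programming specification may hold a rule. Neither document points to one for this purpose. The blinded review in SAP 6.2 decides who is excluded, not which value a result takes. The incomplete third bullet is not counted against the plan.

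**Conclusion.** The omission is real and should be fixed before unblinding. A subject with an adequate no-growth culture at Day 17 belongs to the efficacy population but has no defined primary endpoint value, and the literal derivation removes that subject from the 95% interval because of the outcome.

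The bias can go either way. Under the stated assumptions it is at most about 0.3 log10 for gradual shifts of -1 to -2, and about 1 log10 if 4 of 16 active and 0 of 8 placebo subjects clear from 10^7 with a limit of 10^2. The actual size cannot be derived, because the documents give no limit, SD, baseline distribution or clearance rate. The point does not show that the primary analysis is invalid or that the sponsor intends to drop clearances.

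**What to change.** Before unblinding, add to SAP 9.1 and 9.2.2 a rule such as:

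> A culture from an adequate specimen that grows no *P. aeruginosa* is an observed result below the central laboratory's lower limit. It is set to [one named value tied to that limit, for example the limit itself, in CFU/mL] before log10 transformation, is kept in the primary analysis, and is not missing data.

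Report the number of such results by arm and visit. Add one sensitivity analysis per cohort that either treats them as left-censored (at the log10 limit minus the subject's own log10 baseline) or varies the substituted value.

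In 9.2.2, replace percent change of log10 values with the log10 change and its back-transformed geometric mean ratio. This affects an exploratory summary only.

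If section 13 is corrected, list every departure from the protocol that bears on this analysis:

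- the two conditions added in SAP 6.2;
- the move from Day 17 density in CFU/g to change from baseline in CFU/mL;
- the interval without p-values in place of the test;
- the removal from summary outputs of AP-PA02 subjects enrolled before the first DSMB meeting.

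The cost is SAP wording, one derivation rule, one count table and one sensitivity table, with no new data or visits. The downside is that the estimate depends on the chosen value, and not only slightly (step 5). The value must therefore come from the laboratory's limit and be fixed in advance.
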